## **2.1 Primary Objective (or Aim)**

Specific Aim 1: To test the effectiveness of the Opening Doors to Early Intervention Program on EI service use and child developmental status among poor minority children residing in an urban community

## **2.2 Secondary Objectives (or Aim)**

Specific Aim 2: To assess whether parent engagement mediates the effects of the Opening Doors to Early Intervention Program.

Specific Aim 3: To explore whether the home learning environment, parental health literacy, adverse childhood experiences or poverty moderate the effects of the Opening Doors to Early Intervention Program on child developmental status.

- a. *Aim 3a:* To explore whether differences in developmental scores between intervention and control groups varies by the richness of home learning environments.
- b. *Aim 3b:* To explore whether differences in developmental scores between intervention and control groups varies by the health literacy level of parents.
- c. *Aim 3c:* To explore whether differences in developmental scores between intervention and control groups varies by family income level.

Specific Aim 4: To determine changes in use of and need for safety net programs and adjustment to a remote service delivery model for Early Intervention services among low-income families of children with developmental disabilities during the current COVID-19 pandemic in Philadelphia by way of the COVID-19 Rapid Response Sub-study.

Specific Aim 5: To adapt an already in use evidence-based co-parenting program used nationally in childbirth education settings, for use among caregivers who have experienced significant trauma and chronic stress as a child by way of the Trauma-Informed Co-parenting Sub-study.

### **2.2.1 Consideration of Key Biological Variables**

We will assess the effects of two key biological variables, sex and age, on treatment outcomes. Similar to aim #3 above, we will include sex-by-treatment arm and age group (<18 or  $\geq 18$  months old)-by-treatment arm interaction terms in addition to main effects in models of treatment outcomes. These models will test whether the association between the intervention and outcome differs by sex or age group.

### 3 INVESTIGATIONAL PLAN

#### 3.1 General Schema of Study Design

##### 3.1.1 Randomized Controlled Trial

Families of eligible children will be recruited at the time of an office visit that results in a referral to EI. Recruitment will occur in person or by telephone following an office visit using an electronic recruitment tool that permits clinicians to obtain permission for contact from families at an office visit. Electronic recruitment tools have become standard practice in PeRC and facilitate recruitment of patients across multiple studies. Caregivers of eligible children will be consented in person or remotely by utilizing the REDCap e-consent process, to participate and will complete study visits at baseline, 3 months, 6 months, 9 months, and 12 months (Table 1). We will use all available means including letters, telephone calls, text messages, and emails to ensure data are collected thoroughly and systematically from all participants. Contact information on each participant will be updated every 3 months using interpersonal exchanges and clinic EHR records. Participation incentives will include compensation to complete study measures, quarterly newsletters, and child birthday card mailings, all of which have been used in our prior work with urban populations to maintain >80% participant follow-up.

The study research materials will consist of parent- and observer-reported instruments and EI data. Following written informed consent (which is either completed in person or remotely with the electronic REDCap e-consent process), participant caregivers will complete a baseline visit. Measures of demographic characteristics (child age, sex, race/ethnicity, family income, maternal education level, spoken language, and family structure) (Appendix 2), parental health literacy (SAHL) (Appendix 3), and the home learning environment (StimQ) (Appendix 4) will be collected at this visit. Due to the interactive nature of the SAHL measure, in the event that the baseline visit is conducted remotely, the participant will have the option of either completing the measure of parental health literacy (SAHL) remotely by utilizing a video conferencing application or completing the SAHL in-person at a later date. If a visit is conducted using a video conferencing application, we will try to use a HIPAA-compliant application licensed by CHOP (i.e., Skype, Bluejeans or WebEx). Measures of parent engagement and EI referral and service use will be collected at follow-up visits at 3, 6, 9, and 12 months. These visits will be conducted in-person, by telephone, or by email at the preference of the parent. Parents will be asked at study visits to complete the EI Engagement questionnaire, which was adapted from the CECPS and generated during a prior study (IRB 18-014884), and measures of completion of EI referrals (intake, registration, assignment of service coordinator, home visit, and MDE), eligibility for and initiation of EI services (IFSP), EI services use if eligible (number of EI service visits and whether services were completed or terminated), and use of other services (transfer to Preschool EI services, childcare or preschool enrollment). We will corroborate parent-reported visits with EI staff. Participants will also complete the Philadelphia Expanded ACE measure at one time-point throughout the study. This time-point will typically be the 3-month survey, however the measure may be administered during either the 6- 9- or 12-month follow-up survey time-points in the event that the survey is not completed during the 3-month time-point. The ACEs survey assesses for adverse events in that have already occurred in the past (i.e., childhood adverse experiences),

therefore the variation in time-point of when the ACEs survey is administered is not expected to affect the veracity of the reported responses.

Finally, all children will be assessed for developmental status around 12 months following enrollment at a time before the child turns 42 months 15 days. Parent's and children will have the option of attending the Seashore house on CHOP's main campus or the Robert's Center for Pediatric Research on CHOP's main campus, whichever is most convenient for the participant, to complete a measure of child developmental status (BSID-III) (Appendix 5). If the participant chooses the Seashore House, the Center for Human Phenomic Science will conduct the developmental assessment. If the participant chooses the Robert's Center for Pediatric Research, a clinician will conduct the developmental assessment. In the event in-person procedures cannot take place at the time of the final study visit time-point (due to COVID-19 or other reasons) this assessment may be performed beyond the 12-month time-point, at a later date, anytime before the child turns 42 months and 15 days old. EI data on referral completion, EI referral completion, EI eligibility, and EI services use will be obtained from Philadelphia Infant Toddler Intervention, a community partner on this proposal, to corroborate parent self-report. The Early Intervention data is collected and managed by the Philadelphia Infant and Toddler Early Intervention Program in the Department of Behavioral Health and Intellectual Disabilities Services.

### **3.1.2 COVID-19 Rapid Response Sub-study: Safety Net Program Use Among Low-Income Families of Children with Developmental Disabilities During a Pandemic**

One parent from each of the currently enrolled parent-child dyads in the Main RCT will be contacted by telephone to obtain verbal consent for participation in this sub-study.

Participants consented into the sub-study will be surveyed concerning safety net program use prior to and during the current COVID-19 pandemic. We will also survey these participants concerning current needs that are not addressed by program participation. The survey will be conducted via RedCap at CHOP, which is the method currently used to collect study measures every 3 months. The survey will inquire about current and past year participation in the following safety net programs: unemployment benefits; Medicaid or Children's Health Insurance Program (CHIP); Women, Infants, and Children (WIC); Temporary Assistance to Needy Families (TANF); Supplemental Nutrition Assistance Program (SNAP); Supplemental Security Income (SSI); Early Head Start; and county early intervention services. Questions derived from the latest Survey of Income and Program Participation (SIPP) will be utilized to query participants on program use before and after the onset of the pandemic.

To gain an in-depth understanding of safety net program use, we will conduct telephone interviews with 20-30 parents to identify their perceptions of program assistance and needs. We will inquire about each program they are currently participating in, how services are delivered (e.g. virtually), and whether the current format meets their needs. We will also inquire about barriers and facilitators to program participation and what unmet needs they currently have. An interview guide will be developed for the interviews. All interviews will be audiotaped and transcribed for analysis.

---

RedCap surveys will be exported to a Stata data file for cleaning and analysis. To determine changes in use of services, we will analyze differences in the proportion with past year and current program use to determine changes in demand for individual program services during the COVID-19 pandemic. We will model changes in service use by family income category, race/ethnicity, and education level. Interview transcripts will be analyzed using NVivo, a qualitative software program. Transcripts will be coded, and themes will be generated using a deductive consensus approach and Grounded Theory.

This sub-study will provide important information on current safety net program use and needs among low-income families of children with developmental disabilities during the current COVID-19 pandemic. This information can inform service needs and barriers to access to services for future pandemic planning, when needs are expected to increase due to employment furloughs and layoffs and access to services may be limited by social distancing policies.

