#### **3.3.2 Total Number of Study Sites/Total Number of Subjects Projected**

A total of 410 subjects are anticipated between the two subject groups designated for this study. The first group of subjects will include 360 participants for the Main RCT study, and these subjects will be recruited for the COVID-19 sub-study and also for Phase 2 of the Trauma-Informed Co-parenting Sub-study. The second group of subjects (Delphi Consensus group) will include up to 50 experts that will participate in Phase 1 of the Trauma-Informed Co-parenting Sub-study. Additional descriptions for each study are provided below:

The Main RCT study will be conducted at approximately 4-6 CHOP primary care practices in Philadelphia. Recruitment will stop when approximately 360 subjects are enrolled. It is expected that approximately 360 subjects will be enrolled to produce 300 evaluable subjects.

The COVID-19 sub-study will recruit about 128 participants, one parent from each of the currently enrolled parent-child dyads from the Main RCT.

The Trauma-Informed Co-parenting Sub-study will recruit and enroll a total of around 50 parent participants from the Main RCT and up to 50 experts in childhood trauma.

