#### ***6.4.2.4 Specific Aim 4***

By way of the COVID-19 Rapid Response sub-study, we will determine changes in use of and need for safety net programs among low-income families of children with developmental disabilities during the current COVID-19 pandemic in Philadelphia.

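### Aim 4 reads change in demand from past-year against current programme use; with past year undefined, ordinary turnover can appear as a fall

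*Protocol*

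**What the plan says.** Protocol section 3.1.2 describes one survey of parents from the main trial, covering eight programme categories. It gives the time frame in three ways:

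- The general statement: "Participants consented into the sub-study will be surveyed concerning safety net program use prior to and during the current COVID-19 pandemic".
- The items: "The survey will inquire about current and past year participation in the following safety net programs".
- The questions derived from the Survey of Income and Program Participation (SIPP), which are to "query participants on program use before and after the onset of the pandemic".

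The analysis uses the second of these: "we will analyze differences in the proportion with past year and current program use to determine changes in demand". The Context part of the Abstract repeats that contrast. The next sentence in section 3.1.2 adds: "We will model changes in service use by family income category, race/ethnicity, and education level".

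On numbers, section 3.3.2 says: "The COVID-19 sub-study will recruit about 128 participants, one parent from each of the currently enrolled parent-child dyads from the Main RCT". It gives no derivation.

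The statistical section for this aim (6.4.2.4) says only that "we will determine changes in use of and need for safety net programs among low-income families of children with developmental disabilities". It names no test, significance level or effect size. The SAP stops at Aim 3. No section defines past year, says whether it includes the survey date, or names a paired or unpaired method.

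**The concern.** Past-year participation, as a survey item is normally read, means any use during 12 months. Current participation means status now. These are different quantities. A 12-month figure counts everyone who is on the programme now, plus everyone who was on it at some point and has left. It therefore exceeds the current figure whenever there is turnover, with no change in demand.

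Three consequences follow under that reading:

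- The contrast is biased towards falling use.
- If the window runs up to the survey, every current user is also a past-year user and the difference cannot be positive. Section 3.1.2 itself anticipates, for pandemic planning, that needs rise when people lose work. The stated contrast could not show such a rise.
- Depending on the survey date, the past-year window may contain pandemic months. It is then not a clean period before onset.

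Aim 4 is about change in use and need during the pandemic, so at stake is the sign of its main quantitative result.

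**Working it through.** The plan states no figure for this sub-study, so there is nothing to reproduce. The check asks what the stated contrast returns when nothing has changed.

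**Inputs from the documents:** about 128 parents (section 3.3.2); both answers from the same parent; change taken as the past-year proportion against the current proportion (section 3.1.2).

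**Assumed inputs:** constant current use *p* of 10% to 70%; annual exit *e* (chance that a current user leaves within 12 months) of 5% to 30%; two-sided 5% level; a two-state model in which entries balance exits.

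**Formulas**

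- Exit rate: μ = −ln(1 − *e*)
- Entry rate that keeps *p* constant: λ = μ*p*/(1 − *p*)
- Any use in 12 months: *p* + (1 − *p*)(1 − exp(−λ))
- Spurious fall: (1 − *p*)(1 − exp(−λ))

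At *p* = 0.50, λ = μ, so the fall is 0.5*e*; with *e* = 0.20 that is 0.5 × 0.20 = 10 points. At *p* = 0.10 and *e* = 0.05, μ = 0.0513, λ = 0.0057, and the fall is 0.90 × 0.0057 = 0.5 points.

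Apparent fall in percentage points, with no true change:

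| Current use | Exit 5% | Exit 10% | Exit 20% | Exit 30% |
|---|---|---|---|---|
| 10% | 0.5 | 1.0 | 2.2 | 3.5 |
| 30% | 1.5 | 3.1 | 6.4 | 9.9 |
| 50% | 2.5 | 5.0 | 10.0 | 15.0 |
| 70% | 3.4 | 6.5 | 12.2 | 16.9 |

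The expected fall is the same if the 12-month window ends three months before the survey (an assumed gap), because *p* is constant.

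**Window running up to the survey.** Current minus past-year equals minus the share who used the programme in the year but do not use it now. This is zero or negative by construction. If many families joined and none left, the result would be exactly zero.

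**Does a paired test cure it?** No. In 20,000 simulated surveys of 128 parents at *p* = 0.50 and *e* = 0.20, with no true change, the share of significant results was:

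| Test | Window to survey | Window ending 3 months earlier |
|---|---|---|
| Exact McNemar | 99% | 84% |
| Unpaired z | 21% | 25% |

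The paired test is more precise, so it detects the artefact more often.

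**Like-for-like windows.** With status at one date before onset against status at the survey, the expected difference under no change is 0, and pairing is then an advantage. If 10% of parents change status, the paired standard error is √(0.10/128) = 2.8 points, against √(2 × 0.25/128) = 6.3 points unpaired at 50% use. By a normal approximation to McNemar's test, 128 parents give 80% power for a change of about 7.8, 11.0 or 13.4 points if 10%, 20% or 30% change status (assumed). An unpaired test near 50% use would need about 17.4 points.

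**The case against.** The strongest defence is that the protocol never says past year means any use in 12 months. Section 3.1.2 also speaks of use before and after onset, so past year may be shorthand for status before the pandemic, in which case the items may already be comparable. The questionnaire is not in the documents, so neither reading can be confirmed. That stands, and it makes the bias conditional. It does not rescue the analysis sentence, which names past-year and current use and does not refer to the before/after items.

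A reader might infer that the analysis ignores pairing. The documents do not support this. No test is named, a difference in proportions is also the estimate that accompanies McNemar's test, and modelling changes in service use is compatible with within-parent change. Pairing is unspecified.

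A reader might also attach small p-values to the spurious fall. Those would come from a paired test the protocol has not chosen, at a level it has not stated, with assumed prevalence and turnover. They show what could happen, not what the plan would report.

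Finally, the artefact is small for low-use, low-turnover programmes, and Aim 4 is a secondary, largely descriptive aim supported by interviews. Both points are fair and limit the weight of the concern.

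**Conclusion.** The point holds in conditional form. As written, the contrast for Aim 4 does not measure change in demand unless past year means status at a comparable earlier time, and the protocol does not say that it does. On the ordinary reading, turnover alone gives an apparent fall of 0.5 to 16.9 points across the assumed range, and 2.5 to 15 points at 50% use. If the window includes the survey date, a rise cannot appear at all. The sizes rest on assumed prevalence and exit rates and on a no-change model. The direction needs only the any-use reading and some turnover.

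It would go too far to say that the sub-study is shown to be biased: the wording about onset leaves a comparable reading open. This is a correction worth making before Aim 4 is reported. It does not touch the randomised comparison or the Bayley-III cognitive endpoint.

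**What to change.** 1. In section 3.1.2, the Abstract and section 6.4.2.4, state the contrast as status in one fixed reference month before pandemic onset against status in the survey month, taken from the SIPP-derived before/after items. Reconcile this with the past-year wording.
2. Name a paired analysis: McNemar's test for each programme, with the paired difference and its confidence interval. For the models by income, race/ethnicity and education, use conditional logistic regression or logistic regression with repeated measures per parent. Note that pairing does not remove the bias if the windows differ.
3. If only past-year and current items were collected, report both proportions descriptively, state the reference periods, and do not call the difference a change in demand.

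The cost is wording in the analysis text if the before/after items exist. If they do not and the survey is still open, which the documents do not say, it is at most one extra item per programme. The downside is that parents must recall a specific month.

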### **3.1.3 Trauma-Informed Co-parenting Sub-study**

The proposed study will be conducted in two phases: 1) modified Delphi approach to elicit from parenting, childhood trauma, and co-parenting experts key content that should be included in a primary care based trauma-informed adapted co-parenting program 2) qualitative methods to solicit perspectives from study participants currently enrolled in the Main RCT (R01MD011598) to adapt a primary care based trauma-informed co-parenting program

#### **Phase 1**

Key informants who are nationally or internationally recognized childhood trauma, parenting, and/or co-parenting experts (individuals with a minimum of two peer-reviewed first author manuscripts on the subject matter) will be recruited to contribute to trauma-informed material to be included in the Family Foundations program.

#### **Phase 2**

Parents currently enrolled in the Main RCT, or who were former participants and provided consent to be contacted for future research, will be recruited to participate in a virtual interview using a CHOP approved conferencing software (i.e., BlueJeans or WebEx). Inclusion criteria includes parents with children ages 42 months or younger who report exposure to two or more traumatic or chronic stressors as children. Parental exposure to traumatic and chronic stressors as a child is assessed as part of participation in the parent study using a modified Adverse Childhood Experiences questionnaire

## **3.2 Allocation to Treatment Groups and Blinding**

In this study, 360 eligible children will be randomized 1:1 to the FN or usual care consisting of routine Child Find procedures. We chose a randomized design, because it is most effective at guarding against bias and will ensure that patients in both arms are similar in observed and unobserved characteristics. The initial randomization will be stratified by practice site, child sex, and age group (0-<18 months old and 18-30 months old) to ensure

balance between groups. We will control post-hoc statistically for any imbalances that arise. Allocation concealment (blinding of the treatment assignment) will be implemented using sealed, opaque envelopes, along with stratification, and randomly permuted blocks of unequal sizes (to prevent providers and patients from manipulating the randomization). Treatment assignment will be done at the time of enrollment following informed consent and patients will be followed over time with measures related to EI referral completion, EI services completion, and patient engagement collected at baseline, 3, 6, 9, and 12 months as well as child developmental status around 12 months.

### **3.3 Study Duration, Enrollment and Number of Sites**

#### **3.3.1 Duration of Study Participation**

The Main RCT study duration for the 360 subjects will be approximately 12 months or until the BSID-III is completed (i.e., before the child turns 42 months 15 days).

#### **3.3.2 Total Number of Study Sites/Total Number of Subjects Projected**

A total of 410 subjects are anticipated between the two subject groups designated for this study. The first group of subjects will include 360 participants for the Main RCT study, and these subjects will be recruited for the COVID-19 sub-study and also for Phase 2 of the Trauma-Informed Co-parenting Sub-study. The second group of subjects (Delphi Consensus group) will include up to 50 experts that will participate in Phase 1 of the Trauma-Informed Co-parenting Sub-study. Additional descriptions for each study are provided below:

The Main RCT study will be conducted at approximately 4-6 CHOP primary care practices in Philadelphia. Recruitment will stop when approximately 360 subjects are enrolled. It is expected that approximately 360 subjects will be enrolled to produce 300 evaluable subjects.

The COVID-19 sub-study will recruit about 128 participants, one parent from each of the currently enrolled parent-child dyads from the Main RCT.

The Trauma-Informed Co-parenting Sub-study will recruit and enroll a total of around 50 parent participants from the Main RCT and up to 50 experts in childhood trauma.

